### 3.4 IMM-124E - Hyperimmune Bovine Colostrum

The following summarizes current information on IMM-124E.

#### 3.4.1 Hyperimmune Bovine Colostrum as a Therapeutic

Mammals supply their newborn before birth, at birth or shortly after birth with antibodies, immunocytes and humoral constituents. This “borrowed immunity” is a form of passive immunization to protect the newborn against environmental pathogens until it establishes its own pathogen recognition and disposal systems. In cows, goats, horses and some other animal species, most immunoglobulins are obtained from the colostrum, the first milk after birth, via the gut but in humans the majority of immunoglobulins, and those of the Immunoglobulin(Ig)G-class in particular, are acquired from the mother by placental transport in the weeks prior to parturition [Struff & Sprotte].

Ingested proteins are normally degraded by proteases in the stomach and small intestine to form small peptides and amino acids which are subsequently absorbed. The proteolytic enzymes involved include pepsin, trypsin, chymotrypsin, carboxy-peptidase and elastase which initially degrade antibodies of the IgG type into F(ab')2, Fab and Fc fragments. The F(ab')2 and Fab fragments, however, retain some of their antigen neutralizing activity locally in the gastrointestinal tract [Reilly *et al.* 1997]. In addition the colostrum contains adjuvants which alter the systemic immune system (Adar *et al.* 2012).

### 3.4.2 IMM-124E Composition

IMM-124E is hyperimmune bovine colostrum that is lactose- and fat-reduced. IMM-124E is harvested from the colostrum of dairy cows which have been immunized against the outer antigens, mostly LPS, of the most common strains of Enterotoxigenic *Escherichia coli* (ETEC). This inoculation activates a generalized immune response in the host animal to produce antibody clones which recognize and bind with the bacterial cell-surface epitopes presented. These polyclonal antibodies can also cross-react with other similar bacterial cell surface antigens.

IMM-124E contains approximately 40% IgG in the drug substance, mainly IgG1 and IgA, with small amounts of IgM and IgE. The non-specific nature of the immunoglobulins in IMM-124E and high binding activity against the LPS moiety of ETEC and non-ETEC gram-negative bacteria facilitates the potential for broad protective coverage against these infective agents.

Immuron's IMM-124E-based product, Travelan, has been sold in Australia over-the-counter (for use by adults and children over 6 years of age) at a dose 200 mg three times a day since September 2004. Approximately 140,000 packets (30 tablets each packet) have been sold and no treatment-related adverse events have been reported.

For more information on IMM-124E, please refer to the current Investigator's Brochure

### 3.4.3 Pharmacology

#### 3.4.3.1 *In vitro* Pharmacology

IMM-124E contains anti-LPS antibodies to both the O polysaccharide and lipid A core region of all the serotypes included in the ETEC vaccine. These anti-LPS antibodies also cross-react with both lipid A-core and O-polysaccharide regions of eight other Gram negative bacteria. IMM-124E was able to bind and agglutinate ETEC bacteria *in vitro*. Flagella-specific antibodies present in IMM-124E Drug Substance were able to reduce bacterial motility and adherence to host-cells. For further information, please refer to the Investigator's Brochure.

#### 3.4.3.2 *In vivo* Pharmacology

##### 3.4.3.2.1 Effect of IMM-124E in Leptin Deficient Ob/Ob Mice

In leptin deficient Ob/Ob mice, oral administration of 1mg IgG-enhanced fraction of ETEC colostrum significantly decreased alanine aminotransferase (ALT) ( $p < 0.05$ ) and serum and hepatic triglycerides ( $p < 0.009$  and  $p < 0.05$ , respectively) compared with control animals. Oral administration of the IgG-enhanced fraction of ETEC colostrum induced regulatory T cells and alleviated the chronic inflammatory state in the metabolic syndrome, alleviating insulin resistance and liver injury. For further details, please refer to the Investigator's Brochure.

### 3.4.4 Preclinical Safety

#### 3.4.4.1 *In vitro* Safety

No cytotoxicity or mutagenesis was shown in a Good Laboratory Practice (GLP) AMES study. For further information, please refer to the Investigator's Brochure.

#### 3.4.4.2 *In vivo* Safety

Two short-term, non-GLP, repeat-dose dietary studies were conducted in mice with hyperimmune bovine colostrum powder. There was no indication of treatment-related toxicity in either study.

Freeze-dried hyperimmune bovine colostrum powder (10% w/w, test diet) or milk whey powder (10% w/w, control diet) was added to ground commercial feed for laboratory mice. The test and control batches were pelleted and fed for the duration of the trial (10 days). Mice were divided randomly into four groups (5/sex/group). After a 3-day acclimatization period on the diets, individual mice were

weighed each day and average food consumption was determined. All mice survived and the weight of mice in all four groups increased. Clinical observations did not reveal any adverse effects. There was no significant effect of diet, sex or diet-sex interaction on body weight changes between Days 3 and 10.

A second study was conducted using hyperimmune bovine colostrum powder at the Department of Microbiology, The University of Melbourne, Australia. Five female and five male mice per test group were given a bottle containing either bovine colostrum powder (50mg/mL) or skim milk or water for a total of eight days. All mice showed a steady increase in weight over the eight-day period with no adverse effects on health or behavior between the test and control groups. For further information, please refer to the Investigator's Brochure.

#### 3.4.5 Metabolism and Pharmacokinetics

The pharmacokinetics (PK) and toxicokinetics (TK) of IMM-124E have not been established.

#### 3.4.6 Clinical Trials of IMM-124E

IMM-124E has been studied for the prevention of traveler's diarrhea in three double-blind, randomized, placebo-controlled clinical trials in Europe and the USA, conducted to Good Clinical Practice (GCP) standard. A Phase 1 open label study in NASH has also been conducted.

##### 3.4.6.1 Study 1: Central Public University Hospital, Warsaw, Poland

This was a double-blind, randomized, placebo-controlled, challenge trial with 60 healthy volunteers divided randomly into 4 groups. Each group of 15 was given either one or two IMM-124E or matching placebo tablets 3 times a day (with or without bicarbonate) before meals for 7 days and were then challenged with a pathogenic dose of O78 ETEC ( $1-2 \times 10^9$  bacteria). IMM-124E resulted in significant protection of the volunteers against the development of diarrhea after challenge with pathogenic doses of ETEC, compared with placebo ( $p < 0.01$ ). ETEC O78 was detected in the feces of most volunteers after challenge, independent of treatment, suggesting that the mode of action was blocking the bacteria from binding to the gut epithelium, rather than a bactericidal effect. There were no treatment related adverse events reported. For further information, please refer to the Investigator's Brochure.

##### 3.4.6.2 Study 2: Central Public University Hospital, Warsaw, Poland

This was a double-blind, randomized, placebo-controlled, challenge trial with 30 healthy volunteers randomly assigned to either 400mg IMM-124E or matching placebo tablets 3 times a day before meals for 7 days, before challenge with  $1-2 \times 10^9$  O78 ETEC. Continuing the results of study 1, IMM-124E was significantly more effective ( $p < 0.001$ ) than placebo treatment in protecting the volunteers against the development of diarrhea after challenge with pathogenic doses of ETEC. Bacterial output in stools was not significantly different between placebo and treatment groups. There were no treatment related adverse events reported. For further information, please refer to the Investigator's Brochure.

##### 3.4.6.3 Study 3: Center for Vaccine Development, University of Maryland, Baltimore, Maryland

This was a double-blind, randomized, two-group, placebo-controlled, challenge trial of 22 healthy volunteers. Subjects were treated with ten tablets of active immunoglobulin concentrate containing an equivalent of 1.4 g of colostrum immunoglobulins, or equivalent placebo, taken 3 times a day, with bicarbonate solution. Participants were closely observed by clinical staff. IMM-124E reduced the incidence of diarrhea by 44% following experimental challenge with ETEC strain O78. No treatment related adverse events were reported (Tacket *et al.*, 1988).

#### 3.4.6.4 Phase 1 Clinical Trial of IMM-124E in Patients with NASH, Hadassah Medical Center, Jerusalem

This was an open-label investigator-initiated trial comprising 10 subjects with biopsy proven NASH and insulin resistance; subjects were treated for 30 days with IMM-124E 1800mg daily per orally. Response was determined by changes in liver function tests and metabolic syndrome. Comparison between Day 30 and Day 0 was performed for each patient.

Oral administration of IMM-124E was well tolerated and no treatment-related adverse events were reported. Improvement in markers of insulin resistance were observed though these changes were not statistically significant over 30 days of treatment. A downward trend in HbA1C was observed in a majority of patients. Increases in peripheral blood mononuclear cells (PBMCs) CD4+CD25+, CD4+CD25+Foxp3+ Tregs and in CD4+CD62+ and CD4+CD25+ HLA-DR were also observed.

### 3.5 Rationale

A close interplay exists between the gut and liver. This is based on the evidence that more than 70% of the blood liver supply derives from the portal vein, the direct venous outflow of the intestine [Compare *et al.* 2012].

Disturbances in the homeostasis between bacteria- and host-derived signals at the epithelial level lead to a break in intestinal barrier function and may foster “bacterial translocation”, defined as the migration of bacteria or bacterial products from the intestinal lumen to mesenteric lymph nodes or other extraintestinal organs and sites. While the full repertoire of gut-derived microbial products that reach the liver in health and disease is yet to be explored, the levels of bacterial LPS are increased in the portal and/or systemic circulation in several types of chronic liver diseases, including NASH [Manco *et al.*, 2010]. Derangement of the gut flora, particularly small intestinal bacterial overgrowth, occurs in a large percentage (20-75%) of patients with chronic liver disease. It has been suggested that fatty diets promote gut microbiota changes and endotoxins produced by gram negative bacteria promote the development of NASH [Compare *et al.* 2012].

Hepatic steatosis is commonly associated with factors such as obesity and sub-clinical insulin resistance. Vulnerability to subsequent insults such as endogenous or exogenous toxins increases the production of pro-inflammatory cytokines. This further exacerbates insulin resistance, oxidative stress and organelle dysfunction within liver cells. In addition, circulating LPS has been found to trigger a molecular cascade which results in the release of pro-inflammatory cytokines. The latter eventually leads to hepatocyte death and the accumulation of inflammatory cells seen in NASH. In mice, LPS has also been associated in studies with increase in body weight and accumulated intrahepatic triglyceride [Manco *et al.* 2010].

Bovine colostrum contains increased concentrations of immunoglobulins (mainly IgG) compared with normal cow's milk, presented with other physically protective milk proteins. IgGs are not absorbed into the blood and act in the lumen against bacterial antigens or interact at the mucosal surface with dendritic cells that sample antigens from gut contents, influencing populations of T regulatory lymphocytes.

IMM-124E has strong binding and neutralising activity against a wide range of LPS antigens. It is hypothesised that IMM-124E anti-LPS activity decreases the challenge of LPS to the liver and down-regulates the key T regulatory cell population associated with chronic inflammation and other metabolic defects associated with NASH.

In addition to its potential effect on bacterial translocation, IMM-124E contains adjuvants which promote regulatory T cells that suppress inflammation in target organs. The dual function of this product may be synergistic in alleviating NASH (Adar *et al.* 2012).

A clear unmet medical need remains in the treatment of NASH and an oral, well tolerated treatment for this condition is needed. Bovine colostrum, either as standard or hyperimmune colostrum, has an excellent safety profile [Sarker *et al.*, 1998; Tacket *et al.*, 1992; Mitra *et al.*, 1995; Opekun *et al.*, 1999].

### 3.5.1 Dose Rationale

#### 3.5.1.1 Pharmacodynamic Dose Modeling

Preclinical models of NASH do not provide reliably predictable data for allometric scaling. Further the open-label single-center investigator initiated trial conducted in a small number of subjects (n=10) with type 2 diabetes and NASH (1800mg daily for 30 days) was not of sufficient size or duration to answer whether the response was optimal. Empirically, the 1800mg/day dose will be included in this clinical trial and a higher dose evaluated to establish a dose response curve.

#### 3.5.1.2 Safety Dose Modeling

IMM-124E is well tolerated in clinical studies and in the market place. While the typical dose for traveler's diarrhea is 600mg/day, doses as high as 10g four times daily have been studied. Adverse reactions have been few in number and mild in severity. In most clinical studies of bovine colostrum, there have been no treatment related adverse events reported and no clear pattern in events [Tacket *et al.*, 1992; Shield *et al.*, 1993; Mitra *et al.*, 1995; Sarker *et al.*, 1998; Huppertz *et al.*, 1999; Opekun *et al.*, 1999].

Adverse events observed include:

- nausea, flatulence [Rump *et al.*, 1992; Plettenberg *et al.*, 1993]
- nausea and vomiting in 1/24 patients [Greenberg and Cello 1996]
- mild diarrhea in 1/8 adult volunteers [Lissner *et al.*, 1998]

Tacket *et al.* (1988) reported no adverse clinical signs, but transient moderate elevations in serum levels of hepatic transaminases in volunteers who received bovine immunoglobulin concentrates prepared against *E. coli* (5/10) and rotavirus (2/10). This effect was attributed to diets high in protein provided at the hospital. Colostrum administration should be avoided in person allergic to cow's milk or with lactose intolerance.

The known safety profile of bovine colostrum gives a substantial therapeutic index. Therefore, the highest dose to be evaluated will be 3600mg/day.

### 3.5.2 Discussion of Study Design and Choice of Control Group(s)

A placebo controlled, randomized, double blind design represents the highest standard of clinical trial design available. The study will be multicenter to allow recruitment to occur in a reasonable timeframe. Given the known safety profile of IMM-124E, a parallel design with two dose levels is proposed.

## 4. OBJECTIVES AND ENDPOINTS

### 4.1 Objectives

The primary objectives of this study are to:

- Evaluate the safety and preliminary efficacy of two dose levels of IMM-124E in reducing liver fat evaluated on MRI compared with placebo in subjects with biopsy proven NASH.

The secondary objectives are to:

- Determine the pharmacokinetic profile of IMM-124E;
- Assess the impact of treatment with IMM-124E on markers of glucose metabolism and on serum lipid profile;
- Assess the impact of treatment on liver function over 24 weeks;
- Establish the recommended dose.

Exploratory objectives are to investigate the impact of treatment on potentially relevant immune and metabolic biomarkers associated with NASH.

### 4.2 Endpoints

Safety and efficacy measures for NASH subjects receiving IMM-124E compared with subjects receiving placebo:

#### Primary endpoints:

##### Safety:

- Incidence and severity of adverse events and changes in vital signs and clinical laboratory parameters

##### Efficacy:

- Mean change from Baseline in the percentage fat content of the liver measured by MRI at Week 24

#### Secondary endpoints:

##### Pharmacokinetics:

- Serum concentration of IMM-124E bovine antibodies over time (if measurable) including, but not limited to, maximum observed concentration (Cmax), minimum observed concentration (Cmin) and area under the concentration-time curve (AUC), and, if feasible, elimination half-life (T1/2)

##### Metabolic markers:

- BMI, waist circumference, waist:hip ratio, HBA1C and HOMA-IR
- Serum lipid profile – total cholesterol, triglycerides, LDL and HDL fractions

##### Liver function:

- Mean change from Baseline in serum ALT, AST, bilirubin, albumin and GGT at Weeks 4, 8, 12, 16, 20 and 24
- Proportion of subjects whose ALT at Week 24 is within reference range defined a  $\leq 19$  IU/L for women and  $\leq 30$  IU/L for men
- The proportion of subjects demonstrating a decrease in serum ALT at 24 weeks compared to baseline equal or greater than 30% compared to placebo

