## 8. STUDY DRUGS

### 8.1 Randomization

Subjects will be randomized to one of three treatment groups using a permuted block randomization algorithm supplied by a statistician blinded to patient data.

NASH without insulin resistance or diabetes may be clinically different to NASH with pre-diabetes or diabetes. Equal numbers of patients in each treatment arm is targeted. Randomization will be proportional (1:1:1) and stratified by Baseline HBA1C  $\leq 6.0$  or  $>6.0 - 9.0$ . (See [Section 7.2.2](#) and the Study Reference Manual)

Additionally, to ensure baseline Hepatic Fat Fraction (HFF) would not be a confounding factor, subjects will be stratified for baseline HFF according to the following groups  $\leq 10\%$ ,  $10\% < X \leq 20\%$ ,  $20\% < X < 30\%$  and  $\geq 30\%$ .

If a subject discontinues from the study, the randomization code will not be reused, and the subject will not be allowed to re-enter the study.

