7.2 Primary efficacy analyses

The hepatic fat fraction will be summarised and tabulated for the Baseline and Week 24 visits along with change from Baseline by randomised treatment group. Change in hepatic fat fraction from Baseline will be analysed using analysis of variance on the ITT, PP and FAS populations, where the model will include the treatment group and another subgrouping variable. As determined by baseline values, hepatic fat fraction categories ($\leq 10\%$, $>10\% - <21\%$, $\geq 21\% - <30\%$ and $\geq 30\%$), HbA1c group ($< 6\%$ and $\geq 6\%$), and ALT (greater or less than 1.5 x the upper normal limit) will be used to subgroup the analysis populations. Further, data from liver biopsies up to 6 months prior to screening will also be used to subgroup analysis populations based on fibrosis (0-1 vs. 2-3), NAS inflammation (0-1 vs. 2-3), and NAS ballooning (0-1 vs. 2). These will be used in addition to the main effects factors and the two-way interaction of those main effects.

In the primary analysis, any missing data will remain missing. Treatment effects between placebo and each of the active treatment groups within each of the hepatic fat and HbA1c categories will be generated and tested for significant differences between treatment and placebo using pre-specified contrasts.

To examine the effect of treatment within the various levels of these subgroup variables, a mixed models ANOVA will be employed if there are an appropriate number of observations in each cell (created by the crossing of study treatment and subgroup categories) and the data does not differ significantly from a normal distribution. In the event that this is not the case, the data will be ranked in an attempt to normalise it, and pairwise contrasts between treatment groups will be performed using Wilcoxon rank sum tests within each combination of visit and subgroup variable level will be performed. However, if the ranked data is also not normally distributed, a permutation test will be employed whereby the unranked data will be randomly sampled (Lehmann, 2006). No adjustment for multiple testing will be made. See Appendix 1 for more information on both the Wilcoxon rank-sum test and the permutation test.

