Serum lipid profile values of total cholesterol, triglycerides and high and low density lipoproteins with change from Baseline and number of clinically significant values will be summarised and tabulated by visit and treatment group. Liver function values of ALT, AST, GGT, bilirubin and albumin, with change from Baseline will be summarised and tabulated by visit and treatment group. These liver function tests will also be correlated with HFF, CRP, and A1c. The proportion of subjects with ALT within the normal reference range at Week 24 will be summarised and tabulated by treatment group. Logistic regression modelling will be used to compare proportions in the Placebo group against each of the IMM-124E treatment dose groups using the same model used in the primary efficacy analysis, although the Baseline value of the liver function analyte will be used as a covariate. The area under the curve for change

from Baseline to Week 24, using the Baseline value as reference, for liver enzymes ALT, AST and GGT will also be analysed. For patients in the FAS population who withdraw prior to Week 24, the area under the curve will be adjusted in a manner comparable to a full 24 week period value.

The proportion of subjects demonstrating a decrease in liver percent fat at 24 weeks compared to baseline of 5%, 10%, 20% and 30% respectively will also be analysed. In a similar manner, proportional decreases in ALT, AST and A1c will be assessed using appropriate percentages.

Correlations between change in hepatic fat fraction and changes in ALT, C-reactive protein and A_{1c} will also be calculated.

The Fibrosis-4 Score will be calculated at each visit for which there is data. The formula is $FIB-4 = (Age * AST) / (Platelets / \sqrt{ALT})$. This score will be summarised and tabulated in the same manner as the primary endpoint.

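### The Week 24 normal-ALT endpoint has sex-specific limits but its logistic model has no sex term, which costs modest efficiency in one secondary comparison

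*Protocol*

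**What the plan says.** Protocol 4.2 (Liver function) introduces the endpoint with "Proportion of subjects whose ALT at Week 24 is within reference range defined a" and sets the limits at 19 IU/L or below for women and 30 IU/L or below for men. The synopsis gives the same pair.

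SAP 7.3 gives the analysis: "Logistic regression modelling will be used to compare proportions in the Placebo group against each of the IMM-124E treatment dose groups", continuing "using the same model used in the primary efficacy analysis, although the Baseline value of the liver function analyte will be used as a covariate". No transformation of the Baseline value is mentioned, so the natural reading is ALT in IU/L.

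In the primary model of SAP 7.2, "the model will include the treatment group and another subgrouping variable". The candidates are hepatic fat fraction, HbA1c, ALT, and biopsy fibrosis, inflammation and ballooning. On interactions the SAP adds: "These will be used in addition to the main effects factors and the two-way interaction of those main effects". For the ALT candidate it says "ALT (greater or less than 1.5 x the upper normal limit) will be used to subgroup the analysis populations". Neither document says which upper normal limit is meant.

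Protocol 8.1 says "Randomization will be proportional (1:1:1) and stratified by Baseline HBA1C" and adds four hepatic-fat categories as a second factor. Sex is recorded as a demographic item (Protocol 7.3.1). The table list in SAP 12 has 21 normal-ALT tables (overall and six subgroupings, each in three populations). None is by sex.

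**The concern.** Whether a patient responds depends on how far their ALT starts from their own limit. The two limits differ by a factor of 30/19 = 1.58, so one Baseline ALT value means different things in a woman and in a man. A model that sees ALT but not sex treats the two alike. It leaves explainable variation in the outcome, which costs efficiency. If the arms happen to differ in their share of women, it also has no term to absorb that difference.

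The current inclusion criteria (Protocol 6.2) set no minimum ALT, so patients between the two limits can enroll. Protocol 12.4 asks the SAP to discuss covariates, and the data needed are already collected.

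**Working it through.** **1. Distance from the limit.** The fall needed to respond is 1 − limit/Baseline.
- Baseline 40 IU/L: a man needs 1 − 30/40 = 25%; a woman needs 1 − 19/40 = 52.5%.
- Baseline 25 IU/L: a man already meets the endpoint; a woman needs 1 − 19/25 = 24%.

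**2. What the documents supply.** The only power figure is for MRI liver fat (Protocol 12.1), and it reproduces.
- SD of change = √(6² + 6² − 2 × 0.25 × 6 × 6) = √54 = 7.35, stated as 7.3.
- With 40 per arm and a difference of 5, SE = 7.3 × √(2/40) = 1.632 and 5/1.632 = 3.06.
- Power is 86.5% by the normal approximation and 85.7% by the noncentral t, against a stated figure of about 85%.

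No ALT distribution, responder rate or effect is given, so every ALT input below is an assumption.

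**3. Power.** Simulation inputs: 40 versus 40, half women, log-SD 0.5, Baseline to Week 24 correlation 0.5 to 0.7, median ALT from 30 to 60 IU/L in women and 40 to 60 in men, and a drug effect of 20% to 45%. There were 1,500 trials per setting, with a likelihood-ratio test at two-sided 0.05. The subgrouping term was left out. Model A is treatment plus raw Baseline ALT; model B adds sex. Size-adjusted power uses each model's own simulated 5% critical value. Results at correlation 0.6:

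| Median ALT women/men | Effect | Nominal power A → B | Size-adjusted power A → B |
|---|---|---|---|
| 30/45 | 20% | 36.3% → 39.0% | 32.4% → 34.2% |
| 30/45 | 30% | 77.4% → 78.9% | 73.7% → 74.7% |
| 40/40 | 20% | 31.5% → 36.3% | 31.2% → 33.9% |
| 40/40 | 30% | 66.7% → 73.1% | 66.3% → 71.1% |
| 50/60 | 20% | 23.1% → 25.5% | 16.7% → 18.2% |
| 50/60 | 30% | 51.6% → 54.3% | 42.3% → 45.0% |

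Over all settings, the nominal gain from adding sex was 0.2 to 7.1 points. Another set of runs (correlation 0.6 to 0.75, 30% effect) reached 8.4. The size-adjusted gain was 1.0 to 4.8 points. Dividing Baseline ALT by the patient's own limit performed about as well as adding sex.

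**4. Chance imbalance.** Take the number of women in each arm as binomial(40, 0.5). The probability of a gap of at least 8 women (20 points) is 0.093; of at least 4 (10 points), 0.43. With no drug effect and 24 women on placebo against 16 on drug, the median odds ratio was:
- model A: 1.15 to 1.49;
- model B: 0.98 to 1.05.

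The sign reverses if the imbalance does. Over all randomizations, the median log odds ratio was about 0 in both models.

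**5. Error rate.** Over all randomizations, nominal two-sided size at the three median pairs was 5.9%, 5.3% and 8.5% for A, and 6.8%, 6.3% and 8.5% for B. The excess over 5% reflects few responders (about 4 to 16 per null comparison), not the missing sex term. Given 24 versus 16 women, size-adjusted rejection was 4% to 7% under A and 4% to 5% under B.

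**The case against.** **More than Baseline ALT is in the model.** A reader might infer that the plan adjusts for raw Baseline ALT alone. It does not: a subgrouping variable and its interaction with treatment are also there. If that variable is ALT relative to 1.5 x ULN, and if the limit is sex-specific, it carries part of the missing information. The simulations omit this term. This stands as a limit on the magnitude, although the other five candidates carry no such information by definition.

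**Randomization balances sex in expectation.** A reader might infer that imbalance is systematically read as drug effect, or that false positives rise. Neither is supported. In separate null runs, two-sided error over all randomizations was 5.9% to 7.0% with raw ALT and 6.8% to 7.6% with log(ALT/own limit). Given 24 versus 16 women, raw ALT rejected in 5.3% to 8.1% of trials in one tail but only 0.9% to 1.7% in the other. The two-tailed totals overlapped: 6.7% to 9.8% with raw ALT and 5.4% to 10.8% with the ratio. What remains is a shift in the estimate, conditional on the realised imbalance.

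**The power gain mixes effects.** Part of it reflects the slightly higher size of the adjusted tests. With a log-ratio covariate, another 1 to 2 of 6 to 7 points came from logging ALT. This stands, and the size-adjusted range is the fairer figure.

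**The upper normal limit.** A reader might infer that the ALT subgroup uses a different limit from the endpoint. The limit is undefined, which is not evidence that it differs.

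**Importance.** This is one of many secondary endpoints in an exploratory trial without multiplicity adjustment (Protocol 12). ALT is also analysed by mean change, 30% response and area under the curve, none of which uses these limits. This stands and sets the priority.

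**Conclusion.** The mismatch is plain in the text: sex defines the endpoint but enters neither its model nor the stratification. The consequence is a modest loss of efficiency, about 0 to 8 points of nominal power (about 1 to 5 size-adjusted for adding sex). In a trial with a marked sex imbalance, the estimated odds ratio also shifts, with a median of roughly 1.15 to 1.5 at 24 versus 16 women. A gap at least that large has about 9% probability per comparison.

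All of these sizes rest on assumed ALT medians, spread, correlation and effect, half the patients being women, and a model without the subgrouping term. There is no systematic bias and no inflation of the overall error rate, and the primary MRI analysis is untouched. This is a low-priority improvement.

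**What to change.** In SAP 7.3, for the normal-ALT endpoint only, make one of two changes before unblinding:

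- replace raw Baseline ALT by log(Baseline ALT / limit), with a limit of 19 IU/L for women and 30 IU/L for men; or
- keep Baseline ALT and add sex as a covariate.

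The two are close but not identical. On the log scale, the ratio fixes the sex offset at the ALT slope times ln(30/19) = 0.457, while a sex term estimates it.

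The cost is one sentence and no new data. The ratio uses no extra degree of freedom; the sex term uses one, in a model that may have few events. Because of that sparseness, a small-sample method such as Firth or exact logistic regression may matter at least as much and could be considered alongside.

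Separately, state in SAP 7.2 which upper normal limit the 1.5 x ULN subgroup uses and whether it is sex-specific. Adopting 19 and 30 there would put the cuts at 1.5 × 19 = 28.5 and 1.5 × 30 = 45 IU/L. The effect on cell sizes has not been examined, so the request is for a definition, not for those cuts.
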